4.3 Sub-Study Design and Scope

This sub-study will determine the incidence of externalized conductors and other visual lead anomalies (as evidenced by imaging) and the risk of progression to electrical dysfunction in patients implanted with an Optisure HV lead. A minimum of 200 subjects who consent to participate in this sub-study will undergo cinefluoroscopy (AP, LAO 45° or the best possible LAO view, RAO 45° or the best possible RAO view) at the 24, 36, 48 and 60 month follow-up visits.

Expected Attrition in patients with high voltage leads

Withdrawals due to death

[figure not shown]
Assuming an annual mortality of 7% in the ICD patient population, the mortality at 5 years is 30% $[1 - (1-0.07)^5]$ In the recent RHYTHM ICD/QuickSite 1056K left heart lead study using CRT-D devices, the annual mortality was 12.8%, which would result in a mortality of 49% $[1 - (1-0.128)^5]$ at 5 years. If the ICD:CRT-D device mix is 60%:40% then the expected overall mortality in this study at 5 years is 38% ($=0.6 \times 0.30 + 0.4 \times 0.49$).

Withdrawals due to reasons other than death

In an ongoing St. Jude Medical post-approval study consisting of CRT devices and LV leads, 102 patients have been withdrawn for reasons other than death during an average of 22 months of follow-up. This translates to an attrition of 22% over 5 years.

Assuming that deaths and withdrawals are independent events, the total attrition is expected to be approximately 52% ($= 1 - (1 - 0.38) \times (1 - 0.22)$) over 5 years. With an expected attrition at 5 years to be 52%, a total of 417 subjects who consent to participate in this sub-study will be enrolled in order to have at least 200 subjects with fluoroscopy data available at the 60 month follow-up visit.

4.4 Study Flow Diagram

4.5 Optisure Projected Study Timeline

A timeline for the Optisure Lead Post Approval study is provided below. This timeline may change the actual enrollment rate.

Time = 0; month 1 FDA Approval	Time = month 2	Time = month 3	Time = month 4	Time = month 5	Time = month 6	Time = month 7	Time = month 8	Time = month 9	Time = month 10	Time = month 11	Time = month 12
▪ Study Initiation			▪ 10 sites with IRB approval ▪ First enrollment	▪ Enrollment & follow-up				▪ 60 sites with IRB approval			
			▪ Estimated enrollment = 20	▪ Estimated enrollment = 30	▪ Estimated enrollment = 40	▪ Estimated enrollment = 50	▪ Estimated enrollment = 60	▪ Estimated enrollment = 70	▪ Estimated enrollment = 80	▪ Estimated enrollment = 90	▪ Estimated enrollment = 100
		Cumulative enrollment	▪ 20	▪ 50	▪ 90	▪ 140	▪ 200	▪ 270	▪ 350	▪ 440	▪ 540
Time = month 13	Time = month 14	Time = month 15	Time = month 16	Time = month 17	Time = month 18	Time = month 19	Time = month 20	Time = month 21	Time = month 22	Time = month 23	Time = month 24
▪ Anticipated enrollment of 100/mo after month 12											▪ Enrollment completed
Cumulative enrollment	▪ 740	▪ 840	▪ 940	▪ 1040	▪ 1140	▪ 1240	▪ 1340	▪ 1440	▪ 1540	▪ 1640	▪ 1725
Time = month 25	Time = month 26	Time = month 27	Time = month 28	Time = month 29	Time = month 30	Time = month 31	Time = month 32	Time = month 33	Time = month 34	Time = month 35	Time = month 36
▪ Patient follow-up											
Time = month 37	Time = month 38	Time = month 39	Time = month 40	Time = month 41	Time = month 42	// Elapsed time of 42 months		Time = month 84	Time = month 85	Time = month 86	Time = month 87
▪ Patient follow-up						//		▪ Follow-up completed	▪ Complete Monitoring	▪ Data Analysis	▪ Final report submission

Enrollment for the sub-study (target sample size = 417) is expected to be completed by month 14 assuming that approximately 55% patients will provide consent to participate in the sub-study. Final follow-up visit (60 month visit) in the sub-study is expected to be done in month 84. Results from the sub-study will be included in the progress reports submitted to FDA.

5.0 Study Outcome Measures

5.1 Primary Outcome Measure

5.1.1 Freedom from RV Lead Related Complications

The primary outcome measure for the Optisure Lead Post Approval study is the complication free survival rate at 5 years for complications related to the Optisure RV leads.

The hypothesis is as follows:

H0: Complication free survival at 5 years \leq 92.5%

H1: Complication free survival at 5 years $>$ 92.5%

The desired outcome is to reject the null hypothesis. The null hypothesis will be rejected at the 5% significance level if the 95% Lower Confidence Bound (LCB) for the freedom from complications is greater than 92.5%.

Sample Size

Assuming that the time to first complication follows an exponential distribution and the complication-free survival at 5 years is 95%, a sample size of 645 patients provides 80% power to reject the null hypothesis of 92.5% complication-free survival years at the 5% significance level (See Appendix D for detailed sample size calculations).

Patient Group

All patients who had an attempted implant of the Optisure RV lead will be included in the analysis of this endpoint.

Analysis

All complications will be classified as related to the Optisure RV lead or unrelated.

The following complications will be included in this analysis:

- Cardiac perforation
- Lead dislodgement that occurred greater than 30 days after implant
- Lead insulation damage
- Lead fracture
- Abnormal RV lead performance (abnormal lead defibrillation impedance, abnormal lead pacing impedance, elevated pacing thresholds, loss of capture, failure to deliver therapy, loss of sensing, oversensing, undersensing)

- Other unexpected complications that are considered related to the RV lead

The survival time for all patients will be calculated as the number of days from implant or attempted implant to the date the complication was first discovered. For patients who do not experience a complication related to the Optisure RV lead at the time of their withdrawal, the survival time will be censored on the date of their withdrawal. For patients who have not experienced any complication related to the Optisure RV lead at the time of analysis, the survival time will be censored on the date of analysis. The endpoint will be evaluated using the Kaplan-Meier method and the 95% lower confidence bound (LCB) will be obtained by transformation from its log scale, based on Peto et al¹. The null hypothesis will be rejected if the 95% LCB is greater than 92.5%.

Kaplan-Meier curves will also be presented for each adverse event category of complication listed above.

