5.2 Secondary Outcome Measures

5.2.1 Optisure Lead-Related Complication Rates

The objective is to characterize the complication rate of the Optisure lead, and to perform a trend analysis of all complications. All complications will be evaluated for their relationship to the RV lead, reported and summarized.

The following complications will be reported as related to the RV lead:

- Cardiac perforation
- Lead dislodgement that occurred greater than 30 days after implant
- Lead insulation damage
- Lead fracture
- Abnormal RV lead performance (abnormal lead defibrillation impedance, abnormal lead pacing impedance, elevated pacing thresholds, loss of capture, failure to deliver therapy, loss of sensing, oversensing, undersensing)
- Other unexpected complications that are considered related to the RV lead

Table 1: Summary of RV Lead Related Complications

Description of Complication	Number of Patients with Comp (No. of pts = X)	% of Patients with Comp	Number of Comps	# Comps/pt-years (Total pt-years =)
Cardiac perforation	X	X%	X	X
Lead dislodgement that occurred greater than 30 days after implant	X	X%	X	X
Lead insulation damage	X	X%	X	X
Lead fracture	X	X%	X	X
Abnormal RV lead performance	X	X%	X	X
Other unexpected complications that are considered related to the RV lead	X	X%	X	X
Total	X	X%	X	X

Sample Size

The sample size required to obtain a two-sided 95% upper confidence limit for the complication rate of no more than 5%, based on the Clopper-Pearson exact Binomial method², assuming an expected complication rate of 3.5%, is 828 patients (See Appendix D for detailed sample size calculations).

Sample size accounting for patient attrition

The following categories are included to account for patient attrition.

1. Unsuccessful Implant

A small proportion of the patients are expected to have an unsuccessful implant of the Optisure lead (less than 1%).

2. Mortality

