The expected distribution of ICDs to CRT-Ds in this post-market surveillance study is 3:2³. The annual mortality in the ICD patient population varies between 5.6% and 7%, which are calculated from the published results of the SCD-HeFT and MADIT II trials^{4,5}. Assuming an annual mortality of 7% in the ICD patient population, the mortality at 5 years is 30%. In the recent RHYTHM ICD/QuickSite 1056K left heart lead study⁶, the annual mortality was 12.8%, which gives a mortality of 49% at 5 years. Hence the expected overall mortality in this post-approval study at 5 years is 38% ($=0.6 \times 0.30 + 0.4 \times 0.49$).

3. Withdrawal due to Lost-to-follow-up, system explant due to heart transplant/infection, patient/physician request

In the ongoing St. Jude Medical post-approval study consisting of CRT devices and LV leads⁷, out of a total of 1127 enrollments, 102 patients have been withdrawn for reasons other than death during an average of 22 months of follow-up. This translates to an attrition of 22% over 5 years. It is assumed that attrition in the study over 5 years is 22%. This is a conservative assumption since the CRT Device System Post Approval Surveillance study solely enrolled patients indicated for CRT, while this study is expected to enroll patients receiving either a CRT-D or an ICD.

Assuming that deaths and withdrawals are independent events, the total attrition is thus expected to be approximately 52% ($= 1 - (1 - 0.38) \times (1 - 0.22)$) over 5 years. Thus, a minimum of 1725 patients will be enrolled in the post-approval study.

Patient Group

All patients who give consent for the study and undergo an attempted implant of the Optisure lead or had an Optisure lead implanted within 30 days of enrollment will be included in this analysis.

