Appendix D: Detailed Sample Size Calculations for Complication Free Survival Endpoint

The sample size is calculated assuming that the time to first complication follows an exponential distribution. For a given sample size (N), N samples of time to first complication are generated from an exponential distribution with rate of $(-\log(0.95)/5 = 0.0103)$. The 95% lower confidence bound for the survival probability at 5 years is calculated by transformation from its log-survival scale based on Peto et al. For each sample size N, this is repeated 10,000 times and the power is estimated as the number of times the 95% lower confidence bound is greater than 0.925. This process is repeated and the power is estimated for different values of N, and the sample size is chosen as the smallest N for which the estimated power is $> 80\%$. Simulations were carried out in R version 2.7.1 and the code is provided below:

```

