# Power calculation for exponential assumption
p.nul <- 0.925
p.exp <- 0.95
l.exp <- -log(p.exp)/5

N <- seq(630,660,5)
P <- numeric(length(N))

for (i in 1:length(N)) {
  n <- N[i]
  l <- NULL
  for (j in 1:10000) {
    print(j)
    x <- data.frame(time=rexp(n, l.exp), event=1)
    s.fit <- summary(survfit(Surv(time, event)~1, data=x, conf.int=0.9,
    conf.lower="peto", conf.type="log-log"))
    idx <- sum(s.fit$time<=5)
    l <- c(l, ifelse(idx==0, 1, s.fit$lower[idx]))
  }
  P[i] <- mean(l>p.nul,na.rm=T)
}
res <- cbind(N, P)
dimnames(res)[[2]] <- c("N", "Power")
```

Output:

```
> cbind(N, Power)
[1,] 630 0.8257
[2,] 635 0.8046
[3,] 640 0.7909
[4,] 645 0.8324
[5,] 650 0.8132
[6,] 655 0.8067
[7,] 660 0.8399
```

Detailed Sample Size Calculations for Complication rate

The 95% confidence interval for the Binomial proportion is calculated based on the Clopper-Pearson exact Binomial method. For a given observed value x , of the random variable X , which has a Binomial(n, p) distribution, the 100(1- α)% confidence interval for p is given by (L, U), where ¹:

$$L = \begin{cases} 0 & \text{for } x = 0 \\ \frac{x}{x + (n - x + 1)F_{1-\alpha/2, 2n-2x+2, 2x}} & \text{for } 0 < x < n \\ \left(\frac{\alpha}{2}\right)^{1/n} & \text{for } x = n \end{cases}$$

$$U = \begin{cases} 1 - \left(\frac{\alpha}{2}\right)^{1/n} & \text{for } x = 0 \\ \frac{(x + 1)F_{1-\alpha/2, 2x+2, 2n-2x}}{(n - x) + (x + 1)F_{1-\alpha/2, 2x+2, 2n-2x}} & \text{for } 0 < x < n \\ 1 & \text{for } x = n \end{cases}$$

Simulations for safety endpoint:

For a particular sample size (n), generate 10,000 random binomial samples with $p = 0.4\%$. Calculate the 95% Clopper-Pearson confidence interval for each sample.

The mean of the 95% Upper Confidence Limit is estimated by the average UCL from the 10,000 samples.

The above process was repeated for different values of n , and the sample size was chosen as the smallest n such that the mean 95% UCL is no more than 1% for any sample size larger than n .

Simulations were carried out in R version 2.5.1 and the code is provided below:

```

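### The primary 95% lower bound is written on the log scale, but the sample-size code behind 645 / 80% / 5% uses log-log, so those figures belong to a different bound

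*Protocol*

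**What the plan says.** Section 5.1.1 tests a 5-year complication-free survival of 92.5% with a Kaplan-Meier estimate. It rejects the null hypothesis at the 5% level if the 95% lower bound exceeds 92.5%, and "the 95% lower confidence bound (LCB) will be obtained by transformation from its log scale", citing Peto. On size it states that, if "the complication-free survival at 5 years is 95%, a sample size of 645 patients provides 80% power", and refers to Appendix D.

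The Appendix D text describes the simulated bound as "calculated by transformation from its log-survival scale based on Peto et al". The R code beneath it passes "conf.lower='peto', conf.type='log-log" with a two-sided 90% interval, which is a one-sided 95% bound, and treats every simulated time as an event (no censoring).

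Appendix D also says that "the sample size is chosen as the smallest N for which the estimated power is" above 80%. The printed output gives 0.8257 at 630, 0.8046 at 635, 0.7909 at 640 and 0.8324 at 645.

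Enrolment comes from the secondary endpoint in section 5.2.1: the required number, "assuming an expected complication rate of 3.5%, is 828 patients", is inflated for 52% attrition. "Thus, a minimum of 1725 patients will be enrolled in the post-approval study".

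**The concern.** Log and log-log are distinct transformations of the survival estimate. With survival near 95%, the log bound lies above the log-log bound. The protocol therefore specifies one decision rule and justifies its size, power and significance level with another. An analyst who follows 5.1.1 and one who adapts the Appendix D code would compute different primary bounds. A result falling between them passes 92.5% on one and fails on the other. This is the pass/fail criterion of a post-approval commitment, so the choice should not be left until the data are in.

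**Working it through.** **Inputs.** Null 0.925 and assumed 0.95 (5.1.1); one-sided 95%, z = 1.645, and no censoring (Appendix D code); N = 1725 and 52% attrition over 5 years (5.2.1).

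**Formulas without censoring.** With d events among n patients, S = 1 - d/n. The Peto standard error of log S is SE = sqrt((1-S)/(n-d+1)).
- Log bound: S × exp(-z × SE).
- Log-log bound: exp(-exp(log(-log S) + z × SE/|log S|)).
- With d_max the largest d that still gives a bound above 0.925, power is P(Bin(n, 0.05) ≤ d_max) and type I error is P(Bin(n, 0.075) ≤ d_max).

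**Reproducing the printed table.**

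| N | Printed | Exact, log-log | Exact, log |
|---|---|---|---|
| 630 | 0.8257 | 0.821 | 0.863 |
| 635 | 0.8046 | 0.809 | 0.852 |
| 640 | 0.7909 | 0.796 | 0.879 |
| 645 | 0.8324 | 0.830 | 0.869 |
| 650 | 0.8132 | 0.817 | 0.859 |
| 655 | 0.8067 | 0.805 | 0.885 |
| 660 | 0.8399 | 0.838 | 0.876 |

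Log-log agrees within 0.5 points everywhere, including the dip below 80% at 640. Log is 3.7 to 8.8 points too high and has no dip. The Greenwood variance gives the same d_max at each of these sizes, so this does not depend on how the software applies the Peto option.

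**One result, two verdicts.** N = 645, d = 38:
- S = 607/645 = 0.9411; SE = sqrt(0.0589/608) = 0.00984; z × SE = 0.0162; log S = -0.0607.
- Log: 0.9411 × exp(-0.0162) = 0.9260, reject.
- Log-log: exp(-0.0607 × exp(0.0162/0.0607)) = 0.9238, do not reject.

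So d_max is 38 (log) against 37 (log-log), power 86.9% against 83.0%, and type I error 6.6% against 4.8%.

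**At the planned enrolment.** 828/0.48 = 1725. Kaplan-Meier simulation: 20,000 trials per true value, exponential events, exponential attrition reaching 52% at 5 years (the timing is an assumption), Peto variance.

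| N = 1725, 52% attrition | Log | Log-log |
|---|---|---|
| Type I error | 3.6% | 2.2% |
| Power at a true 95% | 96.1% | 93.6% |

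The log bound is about 0.16-0.17 points higher. The verdicts differ in 1.3% of trials at a true 92.5%, 8.4% at 94%, 5.9% at 94.5% and 2.4% at 95%.

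**Sensitivity at N = 1725.**
- Earlier or later attrition to the same 52%: type I error 3.0-4.3% (log) and 1.8-2.7% (log-log).
- Less attrition: log reaches 5.0% at 22% and 5.9% at none. Log-log is highest with none, at 4.9%.
- Greenwood instead of Peto at 52% attrition: about 6.4-6.6% (log) and 4.9-5.0% (log-log).

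**Selection rule.** 630 and 635 both print above 80%, so 645 is not the smallest qualifying N even on the printed grid. In the exact log-log calculation power first exceeds 80% at N = 581 and stays above it from 641. 645 is thus the first value, on a grid of 5, from which power stays above 80%.

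**The case against.** The written analysis agrees with itself: 5.1.1 and the Appendix D text both say log, and the outlier is one argument in code cited only for sample size. Nothing tells the analyst to reuse that code. The 6.6% belongs to 645 uncensored patients, a trial that will not be run. At 1725 with 52% attrition and the Peto variance the written test is below 5% and well powered, and even at 645 it has more than the claimed 80% power. The code could equally be changed to match the text, leaving the prespecified method alone. The selection-rule slip is separate and concerns a number that does not set enrolment.

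Much of this stands. Enrolment, adequacy of power and, under the planned attrition with the Peto variance, the 5% level are not in danger, and aligning in either direction would be coherent. It does not remove the contradiction: the only evidence offered for 80% power at the 5% level was generated with a bound the protocol does not specify. The written bound's margin below 5% also depends on heavy attrition and on the Peto variance; with little attrition, or with Greenwood, it exceeds 5%.

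**Conclusion.** The concern holds. The text specifies a log-scale bound, the code uses log-log, and the printed output came from log-log. In Appendix D's own setting at N = 645 the written bound has 86.9% power and 6.6% type I error, not about 80% and 5%. At the planned enrolment the consequence is modest: about 0.17 points on the bound, and opposite verdicts in 1.3% to 8.4% of trials at the true rates examined (92.5% to 95%).

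The uncensored figures are exact and do not depend on the variance choice at the sizes tabulated. Those for 1725 rest on exponential event times, assumed attrition timing, and the Peto standard error as given above, which is an assumption about what the software computes. This should be corrected, but it does not call the sample size into question.

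**What to change.** Name one transformation, stated as one-sided, identically in 5.1.1, the Appendix D text and the code. Recommended wording: *the one-sided 95% LCB will be obtained from the log(-log) transformed Kaplan-Meier estimate with the Peto variance*. Change the scale named in the Appendix D text to match.

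Rerun the simulation for that bound at N = 1725 with 52% attrition, and state its type I error (about 2%) and its power (about 94% at a true 95%). Reword the selection rule to *the first grid N from which estimated power stays above 80%*.

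The cost is one sentence in 5.1.1, two in Appendix D and a short simulation, with no change to enrolment. Compared with log, log-log gives up about 2.5 points of power at a true 95% and about 8.4 points at 94%. In return it keeps the 645 justification and, at N = 1725, stays at or below 5% at every attrition level checked (0-52%), and also with Greenwood at 52%.

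If the sponsor prefers log, the code should be changed to log and N, power and type I error restated. Without censoring, power then stays above 80% from N = 531, but type I error over N = 600 to 1725 is 5.5-7.9%, against 3.8-5.3% for log-log.

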5.2 Secondary Outcome Measures

5.2.1 Optisure Lead-Related Complication Rates

The objective is to characterize the complication rate of the Optisure lead, and to perform a trend analysis of all complications. All complications will be evaluated for their relationship to the RV lead, reported and summarized.

The following complications will be reported as related to the RV lead:

- Cardiac perforation
- Lead dislodgement that occurred greater than 30 days after implant
- Lead insulation damage
- Lead fracture
- Abnormal RV lead performance (abnormal lead defibrillation impedance, abnormal lead pacing impedance, elevated pacing thresholds, loss of capture, failure to deliver therapy, loss of sensing, oversensing, undersensing)
- Other unexpected complications that are considered related to the RV lead

Table 1: Summary of RV Lead Related Complications

Description of Complication	Number of Patients with Comp (No. of pts = X)	% of Patients with Comp	Number of Comps	# Comps/pt-years (Total pt-years =)
Cardiac perforation	X	X%	X	X
Lead dislodgement that occurred greater than 30 days after implant	X	X%	X	X
Lead insulation damage	X	X%	X	X
Lead fracture	X	X%	X	X
Abnormal RV lead performance	X	X%	X	X
Other unexpected complications that are considered related to the RV lead	X	X%	X	X
Total	X	X%	X	X

Sample Size

The sample size required to obtain a two-sided 95% upper confidence limit for the complication rate of no more than 5%, based on the Clopper-Pearson exact Binomial method², assuming an expected complication rate of 3.5%, is 828 patients (See Appendix D for detailed sample size calculations).

Sample size accounting for patient attrition

The following categories are included to account for patient attrition.

1. Unsuccessful Implant

A small proportion of the patients are expected to have an unsuccessful implant of the Optisure lead (less than 1%).

2. Mortality

The expected distribution of ICDs to CRT-Ds in this post-market surveillance study is 3:2³. The annual mortality in the ICD patient population varies between 5.6% and 7%, which are calculated from the published results of the SCD-HeFT and MADIT II trials^{4,5}. Assuming an annual mortality of 7% in the ICD patient population, the mortality at 5 years is 30%. In the recent RHYTHM ICD/QuickSite 1056K left heart lead study⁶, the annual mortality was 12.8%, which gives a mortality of 49% at 5 years. Hence the expected overall mortality in this post-approval study at 5 years is 38% ($=0.6 \times 0.30 + 0.4 \times 0.49$).

3. Withdrawal due to Lost-to-follow-up, system explant due to heart transplant/infection, patient/physician request

In the ongoing St. Jude Medical post-approval study consisting of CRT devices and LV leads⁷, out of a total of 1127 enrollments, 102 patients have been withdrawn for reasons other than death during an average of 22 months of follow-up. This translates to an attrition of 22% over 5 years. It is assumed that attrition in the study over 5 years is 22%. This is a conservative assumption since the CRT Device System Post Approval Surveillance study solely enrolled patients indicated for CRT, while this study is expected to enroll patients receiving either a CRT-D or an ICD.

Assuming that deaths and withdrawals are independent events, the total attrition is thus expected to be approximately 52% ($= 1 - (1 - 0.38) \times (1 - 0.22)$) over 5 years. Thus, a minimum of 1725 patients will be enrolled in the post-approval study.

Patient Group

All patients who give consent for the study and undergo an attempted implant of the Optisure lead or had an Optisure lead implanted within 30 days of enrollment will be included in this analysis.

